**Table 10–1: Definitions of Markedly Abnormal Liver Function Values**

Parameter Name	Conventional		Standard		Abnormal Designation
	Unit	Criteria	Unit	Criteria	
Alkaline Phosphatase	U/L	$>5.0 \times \text{ULN}$	U/L	$>5.0 \times \text{ULN}$	AH
ALT	U/L	$>5.0 \times \text{ULN}$	U/L	$>5.0 \times \text{ULN}$	AH
AST	U/L	$>5.0 \times \text{ULN}$	U/L	$>5.0 \times \text{ULN}$	AH
Total Bilirubin	mg/dL	$>3.0 \times \text{ULN}$	umol/L	$>3.0 \times \text{ULN}$	AH
GGT	U/L	$>5.0 \times \text{ULN}$	U/L	$>5.0 \times \text{ULN}$	AH

**Table 10–2: Definitions of Markedly Abnormal Biochemistry Values**

Parameter Name	Conventional		Standard		Abnormal Designation
	Unit	Criteria	Unit	Criteria	
Creatinine	mg/dL	$>3.0 \times \text{ULN}$	mmol/L	$>3.0 \times \text{ULN}$	AH

Parameter Name	Conventional		Standard		Abnormal Designation
	Unit	Criteria	Unit	Criteria	
Glucose	mg/dL	<40 >250	mmol/L	<1.7 >13.9	AL AH
Calcium	mg/dL	>12.5 <7.0	mmol/L	>3.1 <1.75	AH AL
Magnesium	mg/dL	>3.0 <0.9	mmol/L	>1.23 <0.4	AH AL
Potassium	mmol/L	>6.0 <3.0	mmol/L	>6.0 <3.0	AH AL
Sodium	mmol/L	>155 <130	mmol/L	>155 <130	AH AL
Total Cholesterol	mg/dL	>400	mmol/L	>10.34	AH
HDL Cholesterol	mg/dL	<40	mmol/L	<1.04	AL
LDL Cholesterol	mg/dL	≥190	mmol/L	≥ 4.90	AH
Triglycerides	mg/dL	>500	mmol/L	> 5.7	AH

**Table 10–3: Definitions of Markedly Abnormal Hematology Values**

Parameter Name	Conventional		Standard		Abnormal Designation
	Unit	Criteria	Unit	Criteria	
Hemoglobin	g/dL	<8.0 >4.0 above ULN	g/L	<80 >40 above ULN	AL AH
Lymphocytes Absolute	10  /L	<0.5 >20.0	10  /L	<0.5 >20.0	AL AH
Neutrophils Absolute	10  /L	<1.0	10  /L	<1.0	AL
Platelets	10  /L	<50	10  /L	<50	AL
WBC/Leukocytes	10  /L	<2.0 >100	10  /L	<2.0 >100	AL AH

Abbreviations: AH=abnormal high; AL=abnormal low; ALT= alanine aminotransferase; AST = aspartate aminotransferase; dL = deciliter; GGT: gamma-glutamyl transferase; L = liter; mg = milligram; mmol = millimoles; µg = microgram; ULN = upper limit of normal.

The table for markedly abnormal liver function tests (LFTs) will contain data beyond the CTCAE Grade 3 thresholds outlined above in [Table 10–1](#) in order to allow for a more thorough

review of elevated LFTs. There will be one table which will list the count and percentage of subjects meeting the below criteria at any time during the study:

- AST: >3xULN, >5xULN, >8xULN, >10xULN, >20xULN
- ALT: >3xULN, >5xULN, >8xULN, >10xULN, >20xULN
- AST or ALT: >3xULN, >5xULN, >8xULN, >10xULN, >20xULN
- Bilirubin: >1.5xULN, >2xULN

In addition, a table will be produced to summarize potential Hy's Law cases. The following two definitions will be used in that table:

- [AST  $\geq$ 3xULN or ALT  $\geq$ 3xULN] and
- Total Bilirubin  $\geq$ 2xULN in the absence of ALP  $\geq$ 2xULN

In order to meet the above criteria, a subject must experience the elevation in bilirubin and ALT or AST (and the absence of ALP elevation, if applicable) at the same visit. For example, a subject who experiences a  $\geq$ 2 x ULN elevation of bilirubin at one visit and a  $\geq$ 3xULN elevation in ALT (or AST) at a subsequent visit has not fulfilled the Hy's law criteria.

Potential hepatotoxicity (meeting one of the pDILI or Hy's law laboratory criteria at least once) will be considered with and without symptoms potentially associated with hepatitis or hypersensitivity according to the investigator (reported on the Symptoms of Hepatitis and Hypersensitivity CRF page)".

A table for potential drug induced liver injuries (pDILI) will be presented by treatment group for subjects with at least one post-Baseline liver laboratory assessment. Number and percentage of subjects meeting laboratory criteria for pDILI for at least 1 visit and reporting at least 1 symptom potentially associated with hepatitis or hypersensitivity according to the Investigator on the pDILI CRF will be presented. Subjects who potentially meet Hy's law criteria at least 1 time during exposure must meet all criteria at the same visit to be counted as potential Hy's Law.

Spaghetti plots of AST values over time for the subset of subjects with at least one markedly abnormal AST value (CTCAE Grade 3 or 4) will also be presented. A similar set of plots will be produced for ALT values over time for the subset of subjects with at least one markedly abnormal ALT value (CTCAE Grade 3 or 4).

## **10.4 Vital signs, physical findings, and other observations related to safety**

### **10.4.1 Vital signs**

The following vital signs variables should be summarized: systolic blood pressure (mmHg), diastolic blood pressure (mmHg), body temperature (°C) and heart rate (beats/min). The following summary will be provided for the Initial Treatment Period (SS) for Initial and Maintenance Treatment Period, and for the Open-Label Extension Period (OLS). Vital signs will not be summarized for the OLE2.

- A summary of the absolute and change from Baseline value for each vital sign variable by treatment group and visit.

- A shift from Baseline to Post-Baseline systolic and diastolic blood pressure values based on the following categorization will be provided for the Initial and Maintenance Treatment Period (SS), and the Open-label Extension Period (OLS):
  - Hypotension: systolic blood pressure <90 mmHg *or* diastolic blood pressure <60
  - Normal: systolic blood pressure  $\geq 90$  and <120 mmHg *and* diastolic blood pressure  $\geq 60$  and <80 mmHg
  - Elevated: systolic blood pressure between 120-129 mmHg *and* diastolic blood pressure <80
  - Stage 1: systolic blood pressure between 130-139 mmHg *or* diastolic blood pressure between 80-89
  - Stage 2: systolic blood pressure  $\geq 140$  and  $\leq 180$  mmHg *or* diastolic blood pressure  $\geq 90$  and  $\leq 120$  mmHg
  - Hypertensive crisis: systolic blood pressure >180 mmHg *and/or* diastolic blood pressure >120 mmHg.

The following summary will be provided for the Initial Treatment Period (SS), the Initial and Maintenance Treatment Period (SS), and the open-Label Extension Period (OLS):

- A summary of the number and percentage of subjects experiencing at least one markedly abnormal value for a vital sign variable as defined in [Table 10–4](#), by treatment group.

**Table 10–4: Definitions of Markedly Abnormal Blood Pressure Values**

Parameter (unit)	Markedly Abnormal Low	Markedly Abnormal High
Systolic blood pressure (mmHg)	<90 and a decrease from Baseline of $\geq 20$	>180 and an increase from Baseline of $\geq 20$
Diastolic blood pressure (mmHg)	<50 and a decrease from Baseline of $\geq 15$	>105 and an increase from Baseline of $\geq 15$

A by-subject listing of all vital signs data will be provided. This listing will be presented by treatment group and will include center, subject identifier, age, sex, race, weight, visit, vital sign variable and result (with abnormal values flagged as “L” or “H” accordingly). This listing will also be provided separately for the OLE and the OLE2 treatment periods.

#### 10.4.2 Physical examination

Abnormal results of the physical examination together with details of abnormalities: abnormality clinically significant or not, will be listed by subject and visit separately for the Initial and Maintenance (SS), Open-Label Extension (OLS) and Open-Label Extension 2 (OLS2) treatment periods.

#### 10.4.3 Electrocardiograms

ECG data will be analyzed by treatment group and visit for the Initial Treatment Period (SS), the Initial and Maintenance Treatment Period (SS), and by treatment sequence for the Open-Label Extension Period (OLS).

A summary of the number and percentage of subjects with normal and abnormal ECG results, as determined by the central reader, will be presented for all applicable visits.

The following ECG variables will be summarized (absolute values and change from Baseline) by visit: QTcF, RR, PR, QRS and QT.

QTc outliers are defined as QTcF values following dosing that are greater than 450 ms or are increases from Baseline greater than 30 ms. QTcF outliers will be highlighted in the data listings and summarized using the following categories:

- Values >450 ms, >480 ms, >500 ms
- Increase from Baseline of >30 ms, increase from Baseline of >60 ms, increase from Baseline of >90 ms
- Values >450 ms and increases of >30 ms. Values >500 ms and increases of >60 ms

The number and percentage of subjects who meet the ECG outlier criteria at any assessment post first dose will be summarized.

Two separate by-subject listing of all 12-lead ECG data will be provided based on interpretation from central reader and from site.

#### **10.4.4 Other safety variables**

##### **10.4.4.1 Assessment and management of TB and TB risk factors**

A summary of the number and percentage of subjects with negative, positive, and indeterminate IGRA (Interferon-Gamma Release Assay) results at all applicable visits will be presented for the entire study.

A by-subject listing of the “Evaluation of signs and symptoms of tuberculosis” questionnaire data and IGRA results will be provided. This listing will also be provided separately for the OLE and the OLE2 treatment periods.

A by-subject listing of the result of chest x-ray for tuberculosis will be provided by treatment.

##### **10.4.4.2 Electronic Columbia Suicide Severity Rating Scale (eC-SSRS)**

eC-SSRS questionnaire will be self-administered by the subject and assessed by trained study personnel. This scale will be used to assess suicidal ideation and behavior that may occur during the study. Results of the eC-SSRS will be summarized using the number of subject and percentage with (i) events in suicide behavior, (ii) suicidal ideation, (iii) suicidal behavior and ideation, and (iv) self-injurious behavior without suicidal intent.

Suicidal ideation is defined as an event in any of the following 5 categories:

- Wish to be dead
- Non-specific active suicidal thoughts
- Active suicidal ideation with any methods (not plan), without intent to act
- Active suicidal ideation with some intent to act, without specific plan
- Active suicidal ideation with specific plan and intent

Suicidal behavior is defined as an event in any of the following 4 categories:

- Actual attempt
- Interrupted attempt
- Aborted attempt
- Preparatory acts or behavior

Suicidal behavior or ideation is defined as an event in any of the above 9 categories.

Self-injurious behavior without suicidal intent is defined as an event in the category non-suicidal self-injurious injuries.

The incidence of subjects with suicidal ideation, suicidal behavior, suicidal ideation or behavior, and self-injurious behavior will be summarized by treatment group. For events that emerged after 112 days but still within the 140 days window, those events would be classified as treatment emergent, but will be excluded from the output based on the Initial Treatment Period. However, these events will be included in the summaries for Initial Treatment Period and Maintenance Treatment Period combined. Similar summaries will be presented for the Open-Label Extension Period (OLS) by treatment sequence and visit.

A by-subject listing of the eC-SSRS questionnaire data will be provided by treatment group. This listing will also be provided separately for the OLE and the OLE2 treatment periods.

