### **2.3.2 Study periods**

This study will include 5 periods, a Screening Period (2 to 5 weeks), a double-blind Treatment Period (48 weeks; final dose at Week 44), an optional open-label extension (OLE) Period (96 weeks, final dose at Week 136 for subjects receiving bimekizumab 320mg Q8W and at Week 140 for subjects receiving bimekizumab 320mg Q4W, followed by a safety follow-up (SFU) Period (20 weeks after the final dose of IMP). Eligible subjects from US and Canada sites who have completed the OLE Period (at Week 144), including subjects in the SFU period and subjects who have completed the SFU Period will have the option to enroll in the 48-week Open-Label Extension 2 (OLE2) Period followed by a SFU Period (SFU2, 20 weeks after the final dose of IMP administered in the OLE2).

The double-blind treatment Period will be separated into an Initial Treatment Period (16 weeks) and a Maintenance Treatment Period (32 weeks). The end of the study is defined as the date of the last visit of the last subject in the study.

Subjects withdrawing early from the study will undergo the premature end of treatment (PEOT) Visit assessments and will enter the SFU Period. Following completion or early withdrawal from the OLE2 Period, subjects will undergo the SFU of the OLE2 Period (SFU2) and will return for the SFU2 Visit 20 weeks after the last dose of IMP administration in the OLE2 treatment period.

The following study periods are defined for the classification by study period:

- Screening Period: Prior to the date of first dose of study drug
- Initial Treatment Period is defined as the time from the first study drug administration up to the start of the Maintenance Treatment Period
- Maintenance Treatment Period starts with the first study drug administration at or after the Week 16 visit
- Open-Label Extension Period starts with the first study drug administration at or after the Week 48 visit
- SFU Period is 20 weeks after the final dose of IMP in the double-blind Treatment Period or Open-Label Extension Period
- Open-Label Extension 2 Period starts with the first study drug administration at or after the Week 144/OLE2 Baseline visit
- SFU2 Period is 20 weeks after the final dose of IMP in the OLE2.

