### 3.9 Relative day

Relative day will be calculated the following way

- for days on or after the day of first dose of study drug and prior to or on the day of last study drug dose:
  - the current date minus the date of first dose of study drug plus 1 (e.g., the day of first dose will be Day 1).
- for days prior to the first dose of study drug:
  - date of first dose of study drug minus the current date (e.g., the day prior to first dose will be Day -1).
- For days after the last dose of study drug:
  - the current date minus the date of last dose of study drug including a “+” to denote posttreatment days (e.g., the day after the last dose will be Day +1).

Relative day will only be computed for fully completed dates and will be missing for partial dates. Two relative days will be used as follows:

- Compared to the first dose of study drug in the Initial Treatment Period for all subjects
- Compared to the first dose of study drug in the Open-Label Extension 2 Period for subjects in OLS2 only.

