#### Study medication duration (days)

- Date of last active dose of IMP in the Initial Treatment Period – date of first dose + 28 days  
Note: If date of last active dose of IMP in the Initial Treatment Period + 28 days extends to a date beyond the final visit date (including PEOT, but not including SFU), then this calculation reverts to:
  - Final visit date (including PEOT, but not including SFU) – date of first dose + 1.  
Note: If date of last active dose of IMP in the Initial Period + 28 days extends to a date beyond the date of first dose in the Maintenance Treatment Period, then this calculation reverts to:
    - Date of first dose in the Maintenance Period – date of first dose in the Initial Treatment Period + 1.

Note: For subjects who die, if date of last active dose of IMP in the Initial Treatment Period + 28 days extends to a date beyond the date of death, then this calculation reverts to:

- Date of death – date of first dose + 1.

Time at risk (days)

- For subjects who die:
  - Date of death – date of first dose + 1.
- For subjects who complete the final visit of the Initial Period and continue to the Maintenance Period:
  - Date of first dose in the Maintenance Treatment Period – date of first dose in the Initial Treatment Period + 1.
- For subjects who discontinue on or prior to the final visit of the Initial Period, use the minimum of the following:
  - Date of last active dose of IMP in the Initial Treatment Period – date of first dose + 140 days.
  - The total number of days in the Initial Treatment Period (112 days). For AEs that emerged after 112 days but still within the 140 days window, those AEs would be classified as TEAE, but will be excluded from the output based on the Initial Treatment Period. However, these AEs will be included in the AE summaries for Initial Treatment Period and Maintenance Treatment Period combined.
  - Date of last clinical contact – date of first dose + 1.

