### 10.2.2 AE summaries

AE summaries will be provided by actual treatment at the time of the adverse event. Separate AE summaries for OLE2 treatment period will be provided by treatment sequence as specified in Section 3.6 and will be based on OLS2.

For subjects who discontinue on or prior to the final scheduled visit of the Initial Treatment Period, any AEs that emerged more than after 112 days relative to the first dose but still within the 140 days SFU window will be classified as TEAE. However, these AEs will be excluded from AE summaries based on the Initial Period but included in the AE summaries for Initial and Maintenance Treatment Period. See the description of time at risk in Section 10.1.1 for further details.

The following selected outputs will be produced for the SS for the Initial Treatment Period, for the MS for the Maintenance Treatment Period, for the SS for the Initial and Maintenance Treatment Period, for the OLS for the Open-Label Extension Period:

- Incidence of TEAEs – Overview
- Incidence of TEAEs per 100 subject years by SOC, HLT, and PT

- Incidence of Serious TEAEs per 100 subject years by SOC, HLT, and PT
- Incidence of TEAEs Leading to Discontinuation per 100 subject-years by SOC, HLT and PT
- Incidence of TEAEs by decreasing frequency of PT

The following summaries will be provided for the SS for the Initial Treatment Period, for the SS for the Initial and Maintenance Treatment Period:

- Incidence of TEAEs Leading to Death by SOC, HLT, and PT
- Incidence of TEAEs by Maximum Relationship by SOC, HLT, and PT
- Incidence of Serious TEAEs by Relationship, SOC, HLT, and PT – Note: For European Union Drug Regulating Authorities Clinical Trials (EudraCT) reporting purposes
- Incidence of Related Serious TEAEs by SOC, HLT, and PT
- Incidence of TEAEs Leading to Death by Relationship by SOC, HLT, and PT – Note: For EudraCT reporting purposes
- Incidence of TEAEs by Maximum Severity, SOC, HLT, and PT
- Incidence of TEAEs Above Reporting Threshold of 5% by SOC and PT
- Incidence of Non-Serious TEAEs by SOC, HLT, and PT
- Incidence of Non-Serious TEAEs by Maximum Relationship SOC, HLT, and PT
- Incidence of Non-Serious TEAEs Above Reporting Threshold of 5% by SOC and PT
- Incidence of Non-Serious TEAEs Above Reporting Threshold of 5% by Relationship SOC and PT
- Incidence of Related TEAEs by SOC, HLT, and PT
- Incidence of Related TEAEs Above Reporting Threshold of 5% with Risk Differences by SOC and PT

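### The eC-SSRS rule (SAP Section 10.4.4.2) leaves events after 112 days out of the Initial Treatment Period table for all subjects, although the same rule for AEs covers only subjects who discontinue

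*SAP*

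**What the plan says.** **eC-SSRS (Section 10.4.4.2).** "For events that emerged after 112 days but still within the 140 days window, those events would be classified as treatment emergent". The sentence goes on to exclude them from the Initial Treatment Period output. The next sentence reads: "However, these events will be included in the summaries for Initial Treatment Period and Maintenance Treatment Period combined". Neither sentence names a group of subjects.

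**AEs (Section 10.2.2).** The parallel rule opens with a limit: "For subjects who discontinue on or prior to the final scheduled visit of the Initial Treatment Period". Only for those subjects are AEs beyond 112 days from first dose, but within the 140-day follow-up window, kept out of the Initial Period summaries.

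**Time at risk (Section 10.1.1).** The 112-day figure comes from here: "The total number of days in the Initial Treatment Period (112 days"). It is one of three quantities whose minimum is taken, and it is listed only under subjects who discontinue. For subjects who continue, time at risk is "Date of first dose in the Maintenance Treatment Period – date of first dose in the Initial Treatment Period + 1", with no cap.

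**Period definition (Section 2.3.2).** "Initial Treatment Period is defined as the time from the first study drug administration up to the start of the Maintenance Treatment Period". Maintenance starts with the first dose at or after the Week 16 visit.

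**Day count (Section 3.9).** "the day of first dose will be Day 1".

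**Visit window (Section 3.1).** ±3 days is allowed up to Week 24.

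**The concern.** For a subject who stops treatment early, the 112-day cut makes sense: it keeps the off-drug follow-up tail out of a 16-week table. For a subject who goes on to Maintenance there is no such tail. The time between 112 days and the first Maintenance dose belongs to the Initial Period by the SAP's own definition. In practice this means the Week 16 visit itself.

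Without the limit, the eC-SSRS rule cuts into that interval. A finding at a Week 16 visit one to three days late, which is within the permitted window, would be absent from the Initial Period eC-SSRS table. Adjudicated suicidal ideation and behavior TEAEs are also tabulated for the Initial Period (Sections 10.2.3 and 10.2.3.5), under AE rules that have no 112-day cut for continuing subjects. An adjudicated event on the same day would be counted there. Two outputs on one safety topic would then use different period ends.

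The 16-week output compares the two arms as first randomized, before bimekizumab subjects are re-randomized. The assignment of events to it should therefore be unambiguous.

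**Working it through.** **Step 1. Reproduce the SAP's figures.** 16 × 7 = 112 days and 20 × 7 = 140 days, which match the cut and the follow-up window. Section 4.2.1.7.2 sets the scheduled Week 48 visit at first dose + 336 days, and 48 × 7 = 336. By the same convention Week 16 is first dose + 112 days, which is Day 113 under Section 3.9.

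**Step 2. Place the Week 16 visit.** With ±3 days, a permitted visit falls 109 to 115 elapsed days after first dose, or on Days 110 to 116.

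**Step 3. Check whether the 140-day phrase protects continuing subjects.** In Table 7–1 the dose before Week 16 is at Week 12, so the visit is about 4 × 7 = 28 days after the last dose. That is inside 140 days. The phrase does not take continuing subjects out of the rule.

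**Step 4. Compare the rules for a continuing subject seen 114 elapsed days after first dose, before the first Maintenance dose.**

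| Rule | Assignment |
|---|---|
| Section 2.3.2, period definition | Initial Period |
| Section 10.1.1, time at risk | Initial Period (runs to the first Maintenance dose) |
| Section 10.2.2, AE rule | Initial Period (cut does not apply) |
| Section 10.4.4.2, eC-SSRS rule read literally | Left out of the Initial Period output |

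**Step 5. Share of permitted Week 16 visits after the cut.** The SAP does not give the spread of visits, so these are assumptions. They also assume that the eC-SSRS is collected at Week 16 and that events are dated by visit. Let *k* be the visit's offset from nominal, from −3 to +3. The cut takes *k* ≥ 1 if 112 means elapsed days, and *k* ≥ 0 if it means study day.

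| Assumed visit pattern | Elapsed days > 112 | Study day > 112 |
|---|---|---|
| Uniform | 3/7 = 42.9% | 4/7 = 57.1% |
| Triangular (weights 1,2,3,4,3,2,1) | 6/16 = 37.5% | 10/16 = 62.5% |
| 40% on the nominal day, rest even | 30% | 70% |
| 60% on the nominal day, rest even | 20% | 80% |
| 80% on the nominal day, rest even | 10% | 90% |
| Skewed early (weights 7 down to 1) | 6/28 = 21.4% | 10/28 = 35.7% |
| Skewed late (weights 1 up to 7) | 18/28 = 64.3% | 22/28 = 78.6% |

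**Step 6. Date events by onset instead.** Assume onset is uniform over the 28 + *k* days since Week 12 and visits are uniform over the window.

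- Elapsed days: (1/29 + 2/30 + 3/31)/7 = 2.8% of events reported at Week 16.
- Study day: (1/28 + 2/29 + 3/30 + 4/31)/7 = 4.8%.

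**Step 7. Apply the discontinuer limit.** With the limit of Section 10.2.2 in the eC-SSRS sentence, no continuing subject's permitted Week 16 assessment is cut.

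**The case against.** The strongest reply is that the sentence is plainly the discontinuer rule with a phrase lost. It follows the time-at-risk text of Section 10.1.1 almost word for word, with AE terms replaced. Section 10.2.2 also ties the 140 days to safety follow-up, which matters chiefly for subjects who have stopped. This is probably the right account of the intent. It does not remove the defect: nothing in Section 10.4.4.2 restores the limit, and Step 3 shows that a continuing subject meets the wording as written.

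The reply has more force on size. A reader might infer from Step 5 that suicidality disappears from the 16-week table for some 30% to 60% of subjects. The SAP does not support that. The percentages describe hypothetical Week 16 visits after the cut. The incidence changes only for a subject with a positive finding at such a visit and no earlier qualifying event in the period. The SAP does not state that the eC-SSRS is collected at Week 16, that it is done before dosing at that visit, or whether events are dated by assessment or onset. The study-day column is also the weaker reading, because Section 10.2.2 counts 112 days relative to first dose. On elapsed days, a visit exactly on schedule is kept.

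It is also true that nothing is lost from the study report. The events stay in the combined Initial and Maintenance summary and in the by-subject listing, and the summaries are descriptive.

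Finally, a reader might take item (iii), which joins suicidal behavior *and* ideation, as a second composite with its own count. The section defines only the *or* version, any of nine categories, and reports that one. Item (iii) is a loose label.

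**Conclusion.** The point holds as a defect of wording with a definite consequence. Section 10.4.4.2 states the 112-day exclusion without the limit that Sections 10.1.1 and 10.2.2 give it. Applied as written, it contradicts the Initial Period definition for continuing subjects and can make the eC-SSRS table disagree with the adjudicated-event table for the same period.

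The number of affected events cannot be derived from the SAP and is probably small. The 43% figure needs three assumptions: the eC-SSRS is done at Week 16, events are dated by visit, and visits are uniform over the window with elapsed days counted. Other visit patterns and day-count readings give about 10% to 90% of Week 16 assessments. Onset dating gives about 3% to 5% of events reported at Week 16. Both arms fall under the same rule and no between-arm bias is claimed. The effect is that some events may be missing from the Initial Period eC-SSRS table while appearing in the combined one.

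**What to change.** - In Section 10.4.4.2, limit the exclusion to subjects who discontinue on or before the final scheduled Initial Period visit, as Section 10.2.2 does.
- For all other subjects, assign eC-SSRS events to the Initial Treatment Period up to and including the assessment on the day of the first Maintenance dose, before dosing.
- State whether an eC-SSRS event is dated by assessment or by onset.
- As a wording correction only, change item (iii) to *suicidal behavior or ideation*, to match the definition given.

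The cost is a small edit to one section of the SAP and one date condition in the eC-SSRS program. No new data or analyses are needed.
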